2.3.2 KNOWN POTENTIAL BENEFITS

If the participant experiences opioid overdose, the use of the provided or acquired naloxone kit could save their life. Similarly, if the participant encounters a person experiencing opioid overdose, the training and possessed naloxone kit could allow them to save another individual's life. If our hypotheses are confirmed, this study will provide strong preliminary data for a large-scale project to evaluate online recruitment, training, and remote naloxone distribution in a fully powered randomized clinical trial. Demonstrating the effectiveness of this approach could expand access to this life-saving medication and reduce the high and increasing morbidity of opioid overdoses in the United States.

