3 STUDY DESIGN

3.1 OVERALL DESIGN

The primary purpose of this study is to assess the feasibility and acceptability of remote Opioid Overdose Education and Naloxone Distribution (OEND) in order to expand this life-saving intervention to individuals without access to traditional OEND programs. Secondary outcomes include group comparisons of risky opioid use and treatment seeking between participants who receive a naloxone kit and those who do not, as well as differences in active opioid use, severity of use, and past overdose experience between those individuals who elect to participate in overdose education and those who decline. Current or past six-month opioid users will be recruited via Craigslist, complete online screening questions, and an opioid use

survey. After survey completion, all participants will be asked if they would like online naloxone training. Participants interested in completing training will complete a virtual informed consent process, complete training online, and half will receive a naloxone kit in the mail while the other half will be provided information on where to purchase a naloxone kit. Online follow-ups will occur 1, 2, and 3 months after training.

Consent Process: Interested individuals will complete the aforementioned screening questions online through REDCap. Participants who meet the aforementioned inclusion/exclusion criteria will read an informational consent sheet written at a 6th grade reading level. Pressing, “agree to participate” and answering questions on the Opioid Use Questionnaire (described below) will indicate their consent for the anonymous survey. Those participants who complete the online survey and opt in for training will then complete an online informed consent process including a comprehensive overview of the study and encouragement to inquire about any questions or concerns they may have. These participants will receive a secure email link containing the online consent form to read and review. Participants who elect to consent for the study will provide an electronic signature and will receive a PDF of the completed consent form. The investigators will receive a completed consent form, which will be sent electronically.

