7 STUDY ASSESSMENTS AND PROCEDURES

7.1 STUDY ASSESSMENTS

Table 1: Instrument Description

Demographics. Basic demographic information including age, gender, race/ethnicity, education level, employment status, annual income, marital status, living situation, drug allergies, and history of substance use and psychiatric disorders will be collected.

Opioid Use Questionnaire. A questionnaire assessing history of opioid use, experience of personal and observed overdoses, previous experience with naloxone, and past substance use treatment.

Decline Survey. A survey administered to participants who decline to continue with the study and receive opioid overdose and naloxone administration training to evaluate reasons for refusing training.

Pre- and Post-Training Assessment. This scale will be administered pre- and post-viewing of training materials and will assess opioid overdose and naloxone knowledge.

Follow-up Assessment. This scale includes questions about whether the participant has used their naloxone kit, who received the naloxone, who administered the naloxone, whether CPR was performed, whether a call was placed to 911, whether they have experienced personal or observed overdose, whether they have entered substance use treatment, and whether they are currently using opioids in an illicit manner.

Participant Satisfaction Survey. This assessment queries about participants' satisfaction with the online training program and postal distribution of naloxone kits (or information regarding where to obtain a kit).

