8 STATISTICAL CONSIDERATIONS

8.1 STATISTICAL HYPOTHESES

- Primary Efficacy Endpoint(s):

Hypothesis 1 states that remote OEND will be a feasible approach and will be supported if 80 participants are recruited within the first 13 months of the study, there is an overall significant increase in opioid overdose knowledge post-training, 80% of assessment measures are completed, and 80% of participants endorse high satisfaction scores.

- Secondary Efficacy Endpoint(s):

Hypothesis 2 will be supported if there are group differences between individuals who elect to participate in overdose training and those who decline to do so such that individuals who elect to participate will be

more likely to have active opioid use, have higher severity of use, experience of past overdose, and know someone who has experienced an overdose.

Hypothesis 3 will be supported if there are group differences in kit possession and there are no relevant group differences over time (Months 1-3), as quantified by the point estimates of effect size, in behaviors such as risky opioid use and interest/seeking out treatment between participants who received a kit versus those who did not receive a kit.

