8.2 SAMPLE SIZE DETERMINATION

We propose to recruit 80 participants to the training portion of the study over a 12-month period. Sample size was determined by feasibility, since the primary outcomes of the study are feasibility and acceptability of remote OEND. Feasibility and acceptability are operationally defined as 1) recruitment of 80 participants during the first 12 months of the project; 2) increase in opioid knowledge post-training; 3) 80% completion of assessment measures and 4) 80% endorsement of high scores on a participant satisfaction measure. An exploratory aspect of the study involves determining the occurrence of naloxone kit use and outcomes, though the study will not be powered to evaluate this and will serve as a pilot for a larger study. The fundamental purpose of the proposed pilot study is to assess feasibility and acceptability to inform future studies, not to provide sample size estimates. If testing is conducted, assuming recruitment of 80 participants with a dropout rate of 20% (consistent with prior studies), uniformly distributed over the 3-month follow-up period would result in approximately 70 participants on average at each of the three follow-up time points. The sample size provides 80% power to detect a time-averaged mean difference of .55 SD between groups for a continuous outcome, or an odds ratio of 2.69 for a binary outcome, assuming an alpha level of .05 and an intrasubject correlation of .5 (computations in PASS 11 software).

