8.3.3 ANALYSIS OF THE SECONDARY ENDPOINT(S)

Generalized linear mixed-effects models with random effects for subject (and logit links for binary outcomes) will be fitted to the repeated measures data. Linear contrasts will be used to estimate between-group differences. Inverse-link estimates will be computed to facilitate interpretation. A false discovery rate (FDR) approach will be considered to adjust for multiple inferences if necessary. Confidence intervals (possibly adjusted for multiple inferences) will be computed to quantify uncertainty about estimates.

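### Section 8.1 lets the no-difference condition of Hypothesis 3 be met on point estimates alone, with no margin; even an observed difference of zero would leave about ±0.38 SD, or ±15 to ±19 percentage points at assumed event rates of 20% to 50%, not excluded

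*Combined protocol and SAP*

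**What the plan says.** Section 8.1 gives Hypothesis 3 two conditions. The arms must differ in kit possession, and there must be "no relevant group differences over time (Months 1-3), as quantified by the point estimates of effect size" in behaviours for which risky opioid use and interest in or seeking of treatment are given as examples. Neither Section 8.1 nor any other section puts a number on *relevant*, sets a margin, or closes the list of behaviours.

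These comparisons are named outcomes. Section 3.1 states: "Secondary outcomes include group comparisons of risky opioid use and treatment seeking between participants who receive a naloxone kit and those who do not". The follow-up items described in Section 7.1 ask "whether they have entered substance use treatment, and whether they are currently using opioids in an illicit manner", which read as yes/no questions.

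Section 8.2 expects "approximately 70 participants on average at each of the three follow-up time points". It gives the effect detectable with 80% power as "a time-averaged mean difference of .55 SD between groups for a continuous outcome, or an odds ratio of 2.69 for a binary outcome". It gives no power for showing that a difference is absent. Section 8.3.3 fits mixed models to the repeated measures and adds: "Confidence intervals (possibly adjusted for multiple inferences) will be computed to quantify uncertainty about estimates". It does not link those intervals to the rule in Section 8.1.

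**The concern.** A claim of no relevant difference needs evidence that relevant differences have been ruled out. A point estimate near zero cannot supply it, because in a small sample it is compatible with real differences in either direction. With no threshold fixed beforehand, what counts as relevant can also be settled after the results are seen.

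Whether being mailed a kit changes risk behaviour or treatment seeking is a substantive question. Under the rule as written, a report could list Hypothesis 3 as supported beside an interval that leaves the question open. The label also has a stated use. Section 2.3.2 says: "If our hypotheses are confirmed, this study will provide strong preliminary data for a large-scale project".

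**Working it through.** **Inputs.** From Section 8.2: about 70 participants at each of three follow-ups, alpha .05, intrasubject correlation .5. From Section 3.1: 1:1 allocation, so 35 per arm. The documents give no event rate, so 10%, 20% and 50% are assumed below.

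**Reproducing the protocol's figure.** For a time-averaged difference with m = 3 measurements and correlation ρ = .5:

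- Variance factor: [1 + (m − 1)ρ]/m = (1 + 2 × 0.5)/3 = 2/3
- SE = √(2 × (2/3)/35) = 0.195 SD
- Detectable difference at 80% power, two-sided: 2.80 × 0.195 = 0.547 SD

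This matches the stated .55 SD, so the same model can be used for interval width.

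**Continuous outcome, observed difference exactly zero.** The 95% half-width is 1.96 × 0.195 = 0.38 SD. It is ±0.34 SD if the correlation is 0.3 (SE 0.175) and ±0.42 SD if it is 0.7 (SE 0.214). It is ±0.36 SD if all 80 are analysed and ±0.40 SD with 64.

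**Yes/no outcome, observed difference exactly zero.** For event rate p, the risk-difference half-width is 1.96 × 0.195 × √(p(1 − p)), and SE(log OR) = 0.195/√(p(1 − p)).

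| Assumed rate | Risk difference, 95% | SE(log OR) | Odds ratio, 95% CI |
|---|---|---|---|
| 50% | ±19 points | 0.390 | 0.47 to 2.15 |
| 20% | ±15 points | 0.488 | 0.38 to 2.60 |
| 10% | ±11 points | 0.651 | 0.28 to 3.58 |

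These are population-averaged approximations; the mixed logit model of Section 8.3.3 estimates a subject-specific odds ratio.

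Working back from the protocol's odds ratio of 2.69 gives SE = ln(2.69)/2.80 = 0.353 and an interval of 0.50 to 2.00. That is a best case, because 2.69 corresponds to a logistic conversion of the continuous figure (ln(2.69) × √3/π = 0.546 SD), not to a direct calculation at a stated rate. The conclusion does not depend on it.

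**How the rule behaves.** Suppose, for illustration only, that *no relevant difference* meant an observed difference within ±0.2 SD. The rule would be met in 30% of trials if the true difference were 0.3 SD, and in 18% if it were 0.38 SD.

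**What a margin rule could achieve here.** Require the 90% interval to lie within ±M. With truly equal arms, power = max(0, 2Φ(M/SE − 1.645) − 1):

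- Continuous: 0% at M = 0.3 SD, 31% at 0.4 SD, 64% at 0.5 SD, and 80% only near 0.57 SD.
- Odds-ratio margin of 2.0: 25% with the back-solved SE, 10% at a 50% rate, 0% at a 20% rate.

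**The case against.** The strongest reply is that this is a pilot sized on feasibility. Section 8.2 speaks of power only in case testing is done, and describing effect sizes suits that purpose. The intervals are planned, so a reader would see the uncertainty. The label is also joint and secondary: "Hypothesis 3 will be supported if there are group differences in kit possession and there are no relevant group differences over time". And the larger project mentioned in Section 2.3.2 would evaluate recruitment, training and distribution in a powered trial; it is not said to rely on a finding of unchanged behaviour.

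Much of this stands, and it limits the consequence. It does not supply a margin. Section 8.1 goes beyond description by turning point estimates into a condition for support, and a joint condition is no sounder than its weaker half.

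Two points on the figures are also fair. The follow-up items as described are yes/no, so the percentage-point figures are more pertinent than ±0.38 SD. And a 90% interval, the one used for an equivalence claim, is narrower: ±0.32 SD, or ±13 to ±16 points at rates of 20% to 50%. Neither changes the conclusion.

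**Conclusion.** The concern holds. Followed as written, Section 8.1 can count the no-difference condition as met when the trial's own intervals do not exclude about 0.38 SD in either direction, or 15 to 19 percentage points (11 at a 10% rate).

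The figures assume 95% intervals, the time-averaged contrast and the Section 8.2 inputs; the event rates are assumptions. Adjustment for multiple inferences, which Section 8.3.3 allows, would widen the intervals. Covariate adjustment could narrow them for a continuous outcome. The rule should be corrected, but only this secondary conclusion is touched; Hypothesis 1 and the kit-possession comparison stand as they are.

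**What to change.** In Section 8.1, remove the point-estimate rule for the behavioural part of Hypothesis 3 and keep the kit-possession part. Wording such as this would do:

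> Between-arm differences in risky opioid use and in interest in or seeking of treatment over Months 1 to 3 will be described by estimates with 95% confidence intervals. The size of difference not excluded will be stated. No conclusion of no relevant difference will be drawn from the point estimates.

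This costs one paragraph, since Section 8.3.3 already plans the intervals. The downside is that this part of Hypothesis 3 can no longer be declared supported and will usually be reported as inconclusive.

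If the sponsor wants to keep a no-difference claim, then before any comparison by arm it should fix a closed list of outcomes and a justified margin for each, and require the 90% interval to lie within that margin. This costs more and has little power here. For 80% power with truly equal arms, the margin would have to be about 0.57 SD. As an odds ratio it would be about 2.8 (back-solved SE), or 3.1, 4.2 and 6.7 at assumed rates of 50%, 20% and 10%.

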8.2 SAMPLE SIZE DETERMINATION

We propose to recruit 80 participants to the training portion of the study over a 12-month period. Sample size was determined by feasibility, since the primary outcomes of the study are feasibility and acceptability of remote OEND. Feasibility and acceptability are operationally defined as 1) recruitment of 80 participants during the first 12 months of the project; 2) increase in opioid knowledge post-training; 3) 80% completion of assessment measures and 4) 80% endorsement of high scores on a participant satisfaction measure. An exploratory aspect of the study involves determining the occurrence of naloxone kit use and outcomes, though the study will not be powered to evaluate this and will serve as a pilot for a larger study. The fundamental purpose of the proposed pilot study is to assess feasibility and acceptability to inform future studies, not to provide sample size estimates. If testing is conducted, assuming recruitment of 80 participants with a dropout rate of 20% (consistent with prior studies), uniformly distributed over the 3-month follow-up period would result in approximately 70 participants on average at each of the three follow-up time points. The sample size provides 80% power to detect a time-averaged mean difference of .55 SD between groups for a continuous outcome, or an odds ratio of 2.69 for a binary outcome, assuming an alpha level of .05 and an intrasubject correlation of .5 (computations in PASS 11 software).

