8.3 STATISTICAL ANALYSES

8.3.1 GENERAL APPROACH

Data will be exported from REDCap to IBM SPSS statistical software, Version 25 and standard data cleaning procedures will be completed. Study variables for the entire sample will be examined using descriptive statistics such as frequencies and percentages (for categorical variables) and means, standard deviations, percentiles, and ranges (for continuous variables) to ensure values are reasonable. Prior to conducting analyses related to the hypotheses of the study, individual distributions of continuous variables will be examined visually with histograms to confirm that all assumptions for the analyses are reasonably met. Methods robust to distributional assumptions will be used as appropriate. The impact of incorrect data entry will be minimized by the implementation of logic checks in the entry forms on REDCap.

Data analysis for between-group comparisons will begin with descriptive statistics for baseline participant characteristics and outcomes by treatment group. Balance between groups will be assessed using measures of effect size such as the standardized mean difference (Cohen's d) for continuous variables and d -equivalent for binary or categorical variables. Patterns of missing data will be examined according to baseline covariates. Baseline factors that could be causally related to the outcomes and showing relevant between group imbalances or that are predictive of missing data will be used as adjusting covariates. Mixed-effect modeling techniques and covariate adjustment will reduce the impact of missing data, as

the approach allows for using all collected data, and the missing data are considered missing conditionally (on the covariates) at random, a milder assumption than missing completely at random.

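### Section 8.2 claims 80% power for an odds ratio of 2.69, but the basis that reproduces its .55 SD figure gives at most 69–73%

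*Combined protocol and SAP*

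**What the plan says.** Section 8.2 sets 80 participants on feasibility grounds. It then adds a conditional power statement, to apply if testing is done. Recruiting 80 with 20% dropout spread evenly over three months "would result in approximately 70 participants on average at each of the three follow-up time points". With that sample, one sentence claims 80% power for a time-averaged difference of .55 SD in a continuous outcome, or "an odds ratio of 2.69 for a binary outcome, assuming an alpha level of .05 and an intrasubject correlation of .5". Both figures share the same n, alpha and correlation and are attributed to PASS 11.

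Section 8.2 does not state sidedness, the control-arm proportion, the structure of the correlation, its scale for a binary outcome, or whether the odds ratio is marginal or subject-specific.

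The planned secondary analysis is in section 8.3.3: "Generalized linear mixed-effects models with random effects for subject (and logit links for binary outcomes) will be fitted to the repeated measures data". The follow-up items in section 7.1 include several yes/no questions: "whether they have experienced personal or observed overdose, whether they have entered substance use treatment, and whether they are currently using opioids" illicitly.

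**The concern.** Two effect sizes are given the same power under one set of assumptions, so one basis should deliver both. If it delivers the continuous figure but not the binary one, the plan overstates what it can detect on yes/no outcomes. Power for an odds ratio also depends strongly on the control proportion, so a single odds ratio without one cannot be tied to any particular outcome.

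This matters most for between-arm comparisons such as treatment entry and current illicit use. Hypothesis 3 expects no relevant group differences in behaviours of this kind. Overstated sensitivity would make an observed absence of difference look more reassuring than it is, especially for infrequent outcomes.

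**Working it through.** **Inputs.** From 8.2: 80 recruited, 20% dropout uniform over three months, three follow-ups, alpha .05, correlation .5. From 3.1 and 5.1.1: 1:1 allocation. Supplied here because the plan is silent: two-sided test, exchangeable correlation on the observed scale, marginal odds ratio.

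**Attendance.** 80 × (1 − 0.2k/3) for k = 1, 2, 3 gives 74.7, 69.3 and 64.0, mean 69.3. This agrees with the stated figure of about 70, or 35 per arm.

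**Design factor.** (1 + 2 × 0.5)/3 = 0.667, so the effective n per arm is 35/0.667 = 52.5.

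**Continuous figure (reproduces).** SE = √(2/52.5) = 0.195 SD.
- Detectable difference, two-sided: (1.960 + 0.842) × 0.195 = 0.547 SD.
- Power for .55 SD: Φ(0.55/0.195 − 1.960) = 80.5% two-sided, and 88.0% one-sided.

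The stated .55 SD therefore points to a two-sided, exchangeable basis with about 35 per arm.

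**Binary figure, same basis.** Scanning control proportions from 0.01 to 0.99, power for an odds ratio of 2.69 is highest at p₁ = 0.38. There p₂ = 2.69 × 0.38/(0.62 + 2.69 × 0.38) = 0.622, a difference of 0.242.
- Log-OR: SE = √[(1/0.2356 + 1/0.2350)/52.5] = 0.402; Φ(0.990/0.402 − 1.960) = 69.1%.
- Pooled: null SE 0.0976, alternative SE 0.0947; Φ[(0.242 − 1.960 × 0.0976)/0.0947] = 70.6%.
- Unpooled: Φ(0.242/0.0947 − 1.960) = 72.6%.

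Simulation at this best-case proportion (40,000 runs) gave 70–71%.

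| Control proportion | Power for OR 2.69 (three formulas) | OR detectable at 80% (pooled) |
|---|---|---|
| 0.38 (best case) | 69–73% | 3.0 |
| 0.50 | 66–70% | 3.2 |
| 0.20 | 60–64% | 3.3 |
| 0.10 | 42–45% | 4.2 |

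Across the three formulas the best-case detectable odds ratio is 2.95 to 3.12. For 2.69 to reach 80% even at the best proportion, the observed-scale correlation would have to be about 0.27 to 0.34, or n about 42 to 45 per arm.

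**Other readings.**

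| Reading | OR 2.69, best case | .55 SD |
|---|---|---|
| One-sided .05 | 79–82% | 88% |
| AR(1) correlation .5, two-sided | 73–76% | 84% |
| 40 per arm (no dropout), two-sided | 75–78% | 85% |
| Latent-scale .5, marginal OR, two-sided | 76–79% | 80% |
| Latent-scale .5, subject-specific OR, two-sided | about 42% | 80% |

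The latent-scale rows assume a random-intercept logistic model with intercept variance π²/3, which gives a binary-scale correlation of about 0.35 near the best proportion.

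**The case against.** The strongest reply is that this is a reporting gap and not a demonstrated error. The plan leaves several inputs open, and this check fills them in. With logit mixed models planned, reading .5 as a latent-scale correlation is reasonable. With a marginal odds ratio it gives 76–79% while .55 SD stays at 80%. That point stands in part: a reader might infer that the PASS calculation was run wrongly, and the documents do not support this because its output is not included. But the reading gets close to 80% only near the best control proportion, and it needs a marginal odds ratio. The models in 8.3.3 estimate a subject-specific one, for which the same latent-scale reading gives about 42% at best.

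A reader might also infer that 2.69 is a relabelled standardised difference. The logistic conversion of 0.547 SD is exp(0.547 × π/√3) = 2.70, and .55 SD converts to 2.71. Neither is 2.69, and the only place the plan mentions "d -equivalent for binary or categorical variables" is the check of baseline balance in 8.3.1. The documents do not support that origin.

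The second reply is that little depends on the figure, and this stands. Section 8.2 already says the study is not powered for naloxone kit use and its outcomes, and describes the pilot's purpose as "to inform future studies, not to provide sample size estimates". Hypothesis 1 does not use the power statement. The behavioural part of Hypothesis 3 is judged "as quantified by the point estimates of effect size". It would be wrong to infer that the trial is too small for its purpose or that its success criteria are undermined.

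**Conclusion.** The point holds as an inconsistency within one sentence. On the two-sided, exchangeable, 35-per-arm basis that reproduces .55 SD, no control proportion gives an odds ratio of 2.69 the stated 80% power. The ceiling is 69–73%, a shortfall of about 7 to 11 percentage points, and the shortfall widens for less common outcomes. None of the alternative readings tried brings both figures to 80% except approximately, under unstated assumptions and at a favourable proportion.

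The result rests on an observed-scale correlation of .5 and a marginal odds ratio. The 10% and 20% control proportions are illustrative, since the plan gives none. The consequence is confined to how the sensitivity of yes/no comparisons such as treatment entry and current illicit use is described.

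**What to change.** Recheck the binary calculation against the PASS output and amend 8.2 in one of two ways.

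- Restate the binary figure on the same basis as .55 SD, for example: *a marginal odds ratio of about 3.0 at the most favourable control proportion, 3.2 at 50%, 3.3 at 20% and 4.2 at 10% (two-sided .05, exchangeable observed-scale correlation .5)*.
- Keep 2.69 and give its power as about 70% at best on that basis.

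In either case state sidedness, control proportion, correlation scale and structure, and the type of odds ratio. If the PASS output shows that a latent-scale correlation was used, say so, and say whether the odds ratio is marginal or subject-specific, since the two differ from about 76–79% to about 42% at best.

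The cost is a sentence or two in 8.2. Sample size, conduct and success criteria do not change.
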